4. STUDY POPULATION

4.1. Inclusion Criteria

Study participants must satisfy all of the following criteria to be included in the study:

- 1. Sign and date the ICF prior to the start of any study-specific qualification procedures.
- 2. Are male or female participants aged 18 to 75 years at screening.
- 3. Have an established diagnosis of PXE, with typical ocular and dermatological clinical features 1,2:
 - a. Ocular findings angioid streaks or peau d'orange
 - b. Skin findings characteristic PXE papules and plaques or diagnostic histopathological changes in lesional skin
- 4. Are fully vaccinated for coronavirus disease 2019 (COVID-19) per current Center for Disease Control and Prevention guidelines
- 5. For women of childbearing potential (not postmenopausal as a result of either natural or postsurgery cessation of menses), must have a negative serum pregnancy test at screening and must be willing to use an effective method of birth control, as detailed in Section 17.2 upon entering study screening, during the treatment period, and up until the time of the follow-up visit.
- 6. Are willing and able to comply with scheduled visits, drug administration plan, laboratory tests, other study procedures, and study restrictions.

4.2. Exclusion Criteria

Individuals who meet any of the following criteria at screening will be disqualified from entering the study:

- 1. Have a history of bone fracture in the past 6 months.
- 2. Have a history of active metabolic bone disease that significantly affect the interpretation of study biomarker results, excluding osteopenia or osteoporosis without fragility fracture.
- 3. Have a history of calcium pyrophosphate deposit disease such as chondrocalcinosis, pseudogout, and pyrophosphate arthropathy.
- 4. Have a history of hypophosphatasia.
- 5. Have a history of untreated hyperparathyroidism.
- 6. Participated in another interventional research study in the past 60 days.
- 7. Are participating or have participated within the last 12 months in PXE trials (eg, trials with PPi, PPi analogues such as bisphosphonate, or ENPP1 and its analogues) or in clinical trials relating to bone mineralization.

- 8. Used bisphosphonate in the preceding 12 months or had plans to use bisphosphonate during the study.
- 9. Used strong inhibitors or inducers of Cytochrome P450 isozymes, 2C19, 3A4, or 3A5 (Table 17.1 and Table 17.2)
- 10. CGI
- 12. Have an alkaline phosphatase < lower limit of normal (LLN) range
- 13. Have alanine aminotransferase (ALT) or aspartate aminotransferase (AST) >2 × upper limit of normal (ULN) range; total bilirubin >1 × ULN
- 14. Have PLP >ULN
- 15. Have hemoglobin <10.0 g/dL.
- 16. Have a QTcF interval duration >450 ms at screening.
- 17. Have moderate to severe renal insufficiency (Creatinine clearance <60 mL/min by Cockcroft-Gault method).
- 18. Are pregnant or breast-feeding women.
- 19. Are female participants unwilling to use contraceptive methods.
- 20. Have a history of sulfonamide allergy.
- 21. Have any elective surgery planned during the study period.
- 22. Have any other significant condition (medical, psychiatric, social, or medication) that, in the judgment of the Investigator, would prevent full participation or would be inappropriate for the study.

5. STUDY TREATMENT(S)

5.1. Assigning Subjects to Treatments and Blinding

5.1.1. Treatment Group(s)/Sequences

The study will consist of 4 treatment groups in which study drug will be administered in a double-blind, placebo-controlled parallel-group study design (see Figure 3.1).

5.1.2. Method of Treatment Allocation

Eligible subjects will be randomized in a 1:1:1:1 ratio into the 4 treatment groups (DS-1211b or placebo). The randomization schedule will be generated by an independent biostatistician. Prior to treatment, a randomization number will be assigned to each eligible subject. The randomization assignment will be implemented by an automatic voice or web response system.

5.1.3. Blinding

This study will be a double-blind study. Blinding will be applied to all personnel related to the study (subjects, Investigators, and the Sponsor), with the exception of the independent biostatistician and other staff involved in the preparation, release, and shipment of investigational medicinal products.

The independent biostatistician will generate the randomization schedule in accordance with the operating procedure for allocating study drug. Until the study is unblinded, the study drug randomization schedule will be kept securely.

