8.5. Pharmacogenetic (Inherited Genetic) Analysis

9. SAFETY EVALUATION AND REPORTING

9.1. Assessment of Safety Endpoint(s)

The safety endpoints include the following:

- AEs
- ECG findings
- Clinical laboratory test results
- Physical examination/assessment findings
- Hypophosphatasia (HPP) monitoring:
 - Plasma ALP, PLP, PPi, Pi, and Mg
 - Ca (serum and urinary)
 - CC
- Nephrotoxicity monitoring: Serum and urine creatinine, BUN, urine total protein, urine albumin, urine KIM-1, and urine NGAL

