9.2. Adverse Event Collection and Reporting

All AEs (see Section 9.4.1 and Section 9.4.2 for definitions) occurring after the subject signs the Informed Consent Form and up to $14 (\pm 5)$ days after the last dose of study medication (ie, the follow-up period), whether observed by the Investigator or reported by the subject, will be recorded on the Adverse Event CRF page. All SAEs will be followed until resolution, stabilization, the event is otherwise explained, or the participant is lost to follow-up.

Medical conditions (including clinically significant laboratory values/vital signs that are out of range) that were diagnosed or known to exist prior to the consent date will be recorded as medical history, and not an Adverse Event. Exacerbation of a pre-existing medical occurrence and symptom including increase in severity of the symptom will be recorded as an AE on the Adverse Event section.

All AEs and serious adverse events (SAEs) are to be reported according to the procedures in Section 9.5.

All clinical laboratory results, vital signs, and ECG results or findings should be appraised by the Investigator to determine their clinical significance. Isolated abnormal laboratory results, vital sign findings, or ECG findings (i.e., not part of a reported diagnosis) should be reported as AEs if they are symptomatic, lead to study drug discontinuation, dose reduction, require corrective treatment, or constitute an AE in the Investigator's clinical judgment.

At each visit, the Investigator or designee will determine whether any AEs have occurred by evaluating the subject. Adverse events may be directly observed, reported spontaneously by the subject or by questioning the subject at each study visit. Subjects should be questioned in a general way, without asking about the occurrence of any specific symptoms. The Investigator must assess all AEs to determine seriousness, severity, and causality in accordance with the

definitions in Section 9.4. The Investigator's assessment must be clearly documented in the site's source documentation with the Investigator's signature.

Always report the diagnosis as the AE or SAE term. When a diagnosis is unavailable, report the primary sign or symptom as the AE or SAE term with additional details included in the narrative until the diagnosis becomes available. If the signs and symptoms are distinct and do not suggest a common diagnosis, report them as individual entries of AE or SAE.

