For events that are serious due to hospitalization, the reason for hospitalization must be reported as the serious adverse event (diagnosis or symptom requiring hospitalization). A procedure is not an AE or SAE, but the reason for the procedure may be an AE or SAE. Pre-planned (prior to signing the Informed Consent Form) procedures or treatments requiring hospitalization for pre-existing conditions that do not worsen in severity should not be reported as SAEs (see Section 9.4.2 for Definitions).

For deaths, the underlying or immediate cause of death should always be reported as an SAE.

Any serious, untoward event that may occur subsequent to the reporting period that the Investigator assesses as related to study drug should also be reported and managed as an SAE.

COVID-19 assessments are detailed in Section 10.1.

9.3. Combined Elevations of Aminotransferases and Bilirubin and Adverse Events of Special Interest

Combined elevations of aminotransferases and bilirubin, either serious or nonserious and whether or not causally related, meeting the laboratory criteria of a potential Hy's Law case (ALT or AST \geq 3 × ULN with simultaneous total bilirubin [TBL] \geq 2 × ULN) should always be reported to the Sponsor by using a special collection eCRF with the Investigator's assessment of seriousness, causality, and a detailed narrative. ¹⁴ These events should be reported within 24 hours of Investigator's awareness of the event.

If the subject discontinues study drug because of liver enzyme abnormalities, the subject should have additional clinical and laboratory evaluations in order to determine the nature and severity of the potential liver injury.

There are no adverse events of special interest (AESIs) for this study. Hypophosphatasia and nephrotoxicity will be monitored using laboratory alerts and review of AEs reported during this study. Details of HPP and nephrotoxicity monitoring during the conduct of the study are described in the Medical Monitoring Plan.

If the laboratory alerts indicate deterioration of the subject's renal function, the Investigator will be contacted to obtain relevant subject medical history, Investigator's assessment of clinical significance of the results, clinical course, and outcome. Based on the discussion between the Investigator and the Sponsor, further evaluation may be warranted including temporary discontinuation of the investigational product.

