11.8.1. Data Monitoring Committee

A Data Monitoring Committee (DMC) will not be involved in the management of this clinical study.

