12.3. Data Management

Each subject will be identified in the database by a unique subject identifier as defined by the Sponsor.

To ensure the quality of clinical data across all subjects and study sites, a Clinical Data Management review will be performed on subject data according to specifications given to Sponsor/CRO. Data will be vetted both electronically and manually for CRFs and the data will be electronically vetted by programmed data rules within the application. Queries generated by rules and raised by reviewers will be generated within the EDC application. During this review, subject data will be checked for consistency, completeness, and any apparent discrepancies. CRFs queries will be raised and resolved within the EDC application.

Data received from external sources such as central laboratories will be reconciled to the clinical database.

Serious adverse events and nonserious AEs potentially meeting Hy's Law in the clinical database will be reconciled with the safety database.

All AEs will be coded by using MedDRA. Prior and concomitant medications will be coded by using the World Health Organization Drug Reference List.

Data that may potentially unblind the treatment assignment will be handled with special care during the data cleaning and review process. These data will be handled in such a way that, prior to unblinding, any data that may unblind study team personnel will be presented as blinded information or otherwise will not be made available.

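### Does the protocol leave open who may see post-dose ALP, PLP and PPi while the blind is kept?

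*Combined protocol and SAP*

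**What the plan says.** - **Blinding (5.1.3).** Everyone connected with the study is blinded, "with the exception of the independent biostatistician and other staff involved in the preparation, release, and shipment of investigational medicinal products". The section's second paragraph is about generating the randomization schedule and keeping it secure. Section 6.2 describes the blind more briefly and names only subject and Investigator.
- **Masking (12.3).** Before unblinding, "any data that may unblind study team personnel will be presented as blinded information or otherwise will not be made available". The rule sits within data cleaning and review. It names no analyte and does not mention sites.
- **HPP markers (9.1).** The HPP monitoring list includes "Plasma ALP, PLP, PPi, Pi, and Mg". Table 2.1 makes ALP, PPi and PLP primary pharmacodynamic endpoints as well.
- **Alerts (9.3).** "Hypophosphatasia and nephrotoxicity will be monitored using laboratory alerts and review of AEs reported during this study". For declining renal function, "the Investigator will be contacted to obtain relevant subject medical history" and then confers with the Sponsor. HPP alerts have no matching sentence, but "Details of HPP and nephrotoxicity monitoring during the conduct of the study are described in the Medical Monitoring Plan".
- **Investigator duties (9.2, 9.4.1, 9.4.4).** "All clinical laboratory results, vital signs, and ECG results or findings should be appraised by the Investigator to determine their clinical significance". Investigators also decide which abnormal laboratory findings are adverse events (AEs), and an event may be rated related because the drug's pharmacology predicts it.
- **Oversight (11.8.1).** "A Data Monitoring Committee (DMC) will not be involved in the management of this clinical study".
- **Laboratory panel (Table 3.1, 9.8).** The chemistry row of Table 3.1 refers to 9.8 for details, and 9.8 refers back to Table 3.1. Neither lists the chemistry analytes in the readable text.

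**The concern.** These are the markers that TNAP inhibition is expected to move, so a subject's own values could point to active drug. Safety against placebo is a primary objective, and treatment-emergent AEs are tabulated by severity and relationship. An Investigator who saw ALP fall or PLP rise could report or rate the same event differently. Physical examination findings, also a safety endpoint, rest on the examiner's judgment too. Measured laboratory, ECG and pharmacodynamic values do not.

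The sections can also seem to pull against each other. HPP alerts need a reader, but the roles excepted from the blind have no monitoring function and there is no DMC. One person might withhold an HPP value under 12.3 while another expects it to be acted on under 9.3. ALP could in addition reach sites through the chemistry panel, whose contents the readable text does not give.

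**Working it through.** **1. Do the sections contradict one another?** The Medical Monitoring Plan could arrange matters in three ways.

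| Who reads HPP alerts | Conflict with the protocol? |
|---|---|
| A blinded Investigator or Sponsor monitor | Not with 5.1.3: reading a value is not holding the allocation. 12.3 would need an exception only if the values count as unblinding and its rule, set in data cleaning and review, extends to safety alerts. |
| A separate reader, such as central laboratory staff | No. Table 3.1 gives these samples to a central laboratory, which can raise alerts without the code, so 5.1.3 need not list that role. |
| Any reader, with alerts masked | No. 12.3 already provides for blinded presentation, and 9.3 need not repeat it. |

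None of the three forces a contradiction.

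**2. Does 9.2 give Investigators PLP and PPi?** The text does not settle it. Section 9.1 lists HPP monitoring apart from clinical laboratory tests, 11.6.2 puts HPP results under clinical laboratory analyses, and 9.8 names no analytes.

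**3. What can be read?** Section 8.3, Table 3.2, the rows of Table 3.1 after the pharmacodynamic row and one item of the 9.1 HPP list are redacted or missing. A statement on access there cannot be excluded.

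**4. How much could ALP reveal?** There is no figure in the plan to reproduce: 11.9 says the sample size has no statistical basis, and no effect size or variability is given. The falls and CVs below are assumptions.

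Inputs: 1:1:1:1 allocation (5.1.2); two pre-dose values (Visits 1 and 2) and three on-treatment values (Visits 3 to 5) from Table 3.1. Errors are taken as independent and the effect as constant over visits.

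- x = −ln(mean on-treatment / mean pre-dose) / s
- s = √ln(1+CV²) × √(1/n_pre + 1/n_post)
- Placebo: x ~ N(0,1). Dose k: x ~ N(d_k,1), with d_k = −ln(1−fall_k)/s.
- Error of the best guess = ∫ min(0.25 f_placebo, Σ 0.25 f_k) dx. With no values, always guessing active is wrong 25% of the time.

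At CV 15%, s = 0.1492 × √(1/2 + 1/3) = 0.136. For falls of 10, 30 and 50%, d = 0.77, 2.62 and 5.09.

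| Assumed falls | CV 10% (s = 0.091) | CV 15% (s = 0.136) | CV 20% (s = 0.181) |
|---|---|---|---|
| 10/30/50% | 0.141 | 0.178 | 0.201 |
| 5/10/20% | 0.221 | 0.242 | 0.248 |

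At CV 15% with the larger falls, 12%, 75% and over 99% of subjects on the three doses lie outside the placebo 95% limits (|x| > 1.96).

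Those figures use all three on-treatment values, which exist only at Visit 5, whereas AEs are assessed at each visit. With Visit 3 alone, s = 0.1492 × √(1/2 + 1) = 0.183. The error is then 0.202, and about 50% of subjects on the 30% fall lie outside the limits.

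**5. What could one alert reveal?** P(active | alert) = 0.75 f₁ / (0.75 f₁ + 0.25 f₀), where f₁ and f₀ are assumed alert rates on active drug and placebo. With f₁ from 20 to 80% and f₀ from 1 to 10%, an alert raises the 75% prior to between 85.7% (0.150/0.175) and 99.6% (0.600/0.6025). The absence of an alert lowers it to between 37.7% and 72.7%.

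**The case for a change.** The best case for a change is that the markers that carry the dose response also carry HPP safety, and no independent body is named to read them. Section 12.3 covers data that may unblind, so the protocol ought to say whether these values count. A monitoring plan that names the alert recipients would not by itself settle whether 12.3 reaches sites or whether ALP is in the chemistry panel. One sentence and a list of analytes would do it, at no cost in visits, samples or analyses.

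Part of this stands. The readable text gives no access rule for post-dose ALP, PLP and PPi, the cross-reference between Table 3.1 and 9.8 is circular, and a single alert could be informative about treatment. But the request is only to record who sees the values. It proposes no different handling and alters no analysis. If the Medical Monitoring Plan already names the recipients, nothing operational changes either. The circular reference is an editorial slip.

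**Conclusion.** The concern identifies missing detail and does not show a fault in the plan. Section 12.3 supplies the masking principle, 9.3 places HPP monitoring in the Medical Monitoring Plan, and 5.1.3 is consistent with a blinded person reading alerts. Study staff can settle access in that plan without amending the protocol.

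Any bias would fall mainly on Investigator-judged safety: AE reporting, severity and relatedness, and physical examination findings. Its size is unknown. On assumed ALP falls and CVs the error in guessing active versus placebo runs from 14% to 25%, against 25% with no values, so the effect ranges from appreciable to almost nil. That range assumes a guesser who knows the size of each dose's effect and the CV, and that ALP reaches the site at all. The model does not cover PLP or PPi.

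The conclusion rests on two things that could not be checked: that the Medical Monitoring Plan names who receives HPP alerts, as 9.3 implies, and that the redacted or missing text does not conflict with it.

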5.1.4. Emergency Unblinding Procedure

In the case of an emergency where, in the opinion of the Investigator, discontinuation of study drug is not sufficient and the study treatment must be unblinded in order to evaluate further a course of medical treatment, the Investigator can perform the unblinding, after discussion with the Medical Monitor, if possible. Entry of the Adverse Event case report form (CRF) page should be completed before unblinding except in cases where immediate treatment of the subject is required. If immediate treatment is required, the Adverse Event CRF page is to be completed within 24 hours of the unblinding.

In the event of an emergency unblinding, the subject will be informed about his/her treatment assigned. Information about the treatment assignment **must be** restricted to designated study site staff/personnel who are providing immediate care to the subject. Any documentation of the treatment assignment **must be** maintained separately (ie, a secured file). The information **must not be** included in the subject's source files to ensure the treatment assignment will remain blinded to the Contract Research Organization (CRO) monitor and other study personnel not involved with the subject's immediate care.

When an emergency unblinding has occurred, an automatic notification (via e-mail) will be sent to the Investigator and selected Daiichi Sankyo study personnel from the interactive response technology (IRT) vendor. The notification will not contain any unblinding information. This will trigger the follow-up process to document the unblinding by completing the Emergency

Unblinding by Investigator Form (to be provided by study personnel upon receipt of IRT notification) and submission to Daiichi Sankyo Clinical Safety and Pharmacovigilance; please refer to the form for completion instructions.

Once the study treatment has been unblinded for a specific subject, the study treatment should be discontinued for the subject, and the subject should leave the study treatment phase. The end of treatment and follow-up assessments for the subjects will be performed as defined in Section 6.4.

5.2. Study Drug(s)

5.2.1. Description

The study drugs for this study are:

- DS-1211b CCI tablet CCI
- Matching placebo tablets

5.2.2. Labeling and Packaging

DS-1211b tablets and matching placebo tablets will be supplied by the Sponsor. The study drug will be labeled in compliance with regulatory requirements and packaged in double-blinded wallets. The packaging will be clearly labeled "For Clinical Study Use Only," and will display the lot number, storage condition, protocol number, and other required information in accordance with local regulations. Study drug will be assigned via an IRT.

5.2.3. Preparation

All study drugs will be supplied as tablets that need no further preparation at the study sites.

5.2.4. Administration

Study drug is to be administered once daily dosing in the morning either in the fasted state or with a meal.

5.2.5. Storage

Drug supplies must be stored in a secure, limited-access storage area under the recommended storage conditions.

If storage conditions are not maintained per specified requirements, the Sponsor or CRO should be contacted.

5.2.6. Drug Accountability

When a drug shipment is received, the pharmacist or designee will check the amount and condition of the drug against the shipping documentation. The pharmacist or designee shall contact the Sponsor as soon as possible if there is a problem with the shipment.

The Receipt of Shipment Form should be emailed as instructed on the form unless receipt is controlled by an IRT. The original will be retained at the study site.

In addition, the Investigator or designee shall contact Sponsor as soon as possible if there is a problem with the shipment.

Drug Accountability will be conducted via the IRT or local site procedures for study drug, placebo, and commercial product as appropriate. The record must be kept current and should contain the dates and quantities of study drug received, subject's identification number (with or without initials) and supply number as applicable, the person for whom the study drug was dispensed, the date and quantity of study drug dispensed and remaining, and the initials of the dispenser.

The pharmacist (or qualified designee) is responsible for study drug accountability, reconciliation, and record maintenance (ie, Receipt of Shipment Form, dispensation/return record, and certificate of destruction/return receipt).

At the end of the study (or as directed), all unused or partially used study drug will be returned or destroyed as per local laws or site policy and only after the CRO monitor has completed a final inventory. If applicable, the return of study drug must be documented, and the documentation must be included in the return shipment.

Please see the Pharmacy Manual for more details.

